2.2.3 Clinical activity and Safety of ibrutinib

Ibrutinib was tested in a phase I, multicenter, open-label, dose escalation study in patients with recurrent NHL.(14) The objectives included studying the safety profile of ibrutinib, identifying the maximum tolerated dose (MTD) and optimal dosing schedule, and characterizing efficacy, pharmacokinetics, and pharmacodynamics. A minimum of 6 subjects per cohort received 1 of 5 escalating dose levels of ibrutinib between 1.25 and 12.5 mg/kg for 28 consecutive days in a 35-day cycle. There was a pre-specified objective of escalating 3 dose levels above that which achieved full BTK occupancy based on the fluorescent probe assay.

A total of 66 patients were evaluated in this study. Two additional cohorts received a continuous ibrutinib dose of 8.3 mg/kg without a 7-day rest and a fixed continuous dose of 560 mg/day. Full BTK occupancy was achieved with doses ≥2.5 mg/kg/day. A dose of 12.5 mg/kg/day was the highest dose cohort evaluated. There were 2 dose-limiting toxicities (DLTs) (Grade 2 neutropenia [2.5 mg/kg/day] and Grade 3 hypersensitivity [8.3 mg/kg/day]) in separate cohorts. The maximum tolerated dose (MTD) of ibrutinib in subjects with B-cell malignancies was not established in this study. Five of 15 subjects with DLBCL (33%) achieved objective responses, 2 CRs and 3 partial responses (PRs). The median

time on treatment was 8 weeks (range: 2 to 98 weeks). Median PFS was 2.5 months (range: 0.7 to 4.6 months) and the median follow-up time was 3.5 months (range: 0.8 to 22.5 months).

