A subsequent phase I/II, multicenter, open-label, and single-arm study in subjects with rel/ref DLBCL was performed. (15)In order to determine whether ibrutinib had subtype specificity subjects enrolled were retrospectively analyzed into cohorts by subtype, either activated B-cell like (ABC) versus germinal B-cell like (GCB). Subtype analysis was performed by gene expression profiling (GEP). In this study all subjects received a starting dose of ibrutinib at 560 mg/day. The objectives of this study included the determining the safety of this dosing regimen and an assessment of efficacy of ibrutinib in DLBCL. Eighty subjects were enrolled and evaluable for response. The overall response rate (ORR) was 25% (20/80 subjects). In the ABC subtype, ORR was 37% (14/38 subjects; Only 1 PR (5%) was observed in the 20 patients retrospectively determined to be of GCB subtypes. Thus, while the 2 subgroups were retrospectively assigned, ibrutinib may be less active in rel/ref DLBCL, GCB subtype.

The most common adverse reactions (>=25%) in pts with B cell malignancies (MCL, CLL, WM) were thrombocytopenia, neutropenia, diarrhea, anemia, fatigue, musculoskeletal pain, bruising, nausea, upper respiratory tract infection and rash.

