An efficacy-stopping rule is also in place for the combination. After testing the combination on 12 patients, the trial will be terminated if </= 1 patients respond. If the trial goes on to the second stage and not discontinued due to the CTE stopping rules prior to, a total of 24 patients will be studied. If the total number responding is less than or equal to five, the regimen will be rejected. This follows a Simon two-stage design for efficacy following a minimax design with the following parameters: overall response rate for a poor regimen of 0.01, overall response rate for a good regimen of 0.31, a type I error of 0.20 and power of 80%.

Efficacy measures which will be determined include ORR, TTR, DOR, and PFS. ORR is defined as the percentage of patients achieving a best response of CR/CR, PR at any disease assessment time point. TTR is defined as the time or number of cycles between study registration and documentation of first response (CR/Cru, or PR). DOR is defined as the time or number of cycles between documentation of first response and progression, change of therapy, death, or date of last contact (if still alive without progression). PFS is defined as the time between study registration and documented progression or death if no progression was observed.

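### The printed Simon inputs do not generate the 1/12, 5/24 efficacy rule, and the stated null rate and type I error do not describe it

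*Combined protocol and SAP*

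**What the plan says.** The efficacy rule is in Section 10.0 (Statistical Considerations), after the toxicity stopping rule. The first-stage rule is "After testing the combination on 12 patients, the trial will be terminated if </= 1 patients respond". Otherwise 24 patients are studied, and "If the total number responding is less than or equal to five, the regimen will be rejected". Section 10.0 then gives the origin of the rule: "This follows a Simon two-stage design for efficacy following a minimax design with the following parameters". The inputs it lists are "overall response rate for a poor regimen of 0.01, overall response rate for a good regimen of 0.31, a type I error of 0.20"; the target power is 80%. Toxicity and efficacy are both assessed in the whole cohort, so the group split does not enter the calculation. No other null rate, error rate or derivation for this rule appears in the documents. Response rate is a secondary objective (Section 1.0); the primary objective is safety and tolerability.

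**The concern.** A null of 1% and an alternative of 31% are so far apart that very few patients separate them, above all with a type I error as loose as 0.20. Under the null, 24 patients would yield 24 × 0.01 = 0.24 responses on average, yet the rule demands at least six. The inputs and the rule therefore looked as if they belonged to different designs.

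This is the plan's only formal efficacy rule. It can end the trial at 12 patients, and it decides whether the regimen counts as rejected in a study meant to inform a later, properly powered trial. The null rate and the type I error tell a reader what passing shows. Taken at face value, a 1% null makes a pass look almost impossible by chance, when the rule passes quite often at response rates that are still modest.

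**Working it through.** **Inputs (all from Section 10.0).** p0 = 0.01, p1 = 0.31, type I error 0.20, power 0.80. Rule: n1 = 12, r1 = 1, n = 24, r = 5.

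**Formulas.** With X1 responses in the first 12 patients and X2 in the next 12, both binomial with rate p:
- P(stop at 12) = P(X1 ≤ 1)
- P(pass) = Σ over x1 ≥ 2 of P(X1 = x1) × P(X2 > 5 − x1)

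Type I error is P(pass) at p0; power is P(pass) at p1.

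**Step 1: the stated power, at p = 0.31.**
- x1 = 2: 0.1552 × 0.5381 = 0.0835
- x1 = 3: 0.2324 × 0.7704 = 0.1790
- x1 = 4: 0.2349 × 0.9256 = 0.2174
- x1 = 5: 0.1688 × 0.9884 = 0.1669
- x1 ≥ 6: 0.1343

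The sum is 0.781, against 0.80 stated. The rule reaches 0.80 at a response rate of 0.3165.

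**Step 2: the stated type I error, at p = 0.01.**
- x1 = 2: 0.005969 × 4.64e-6 = 2.77e-8
- x1 = 3: 2.010e-4 × 2.056e-4 = 4.13e-8
- x1 = 4: 4.568e-6 × 0.006175 = 2.82e-8
- x1 = 5: 7.38e-8 × 0.1136 = 0.84e-8
- x1 ≥ 6: 0.09e-8

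The sum is 1.065e-7, against 0.20 stated. Ignoring the first-stage stop (1.15e-7), setting r1 = 0 (1.15e-7) or setting r = 4 (3.1e-6) does not bring it near 0.20.

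**Step 3: the minimax design for the stated inputs.** A full search over (r1, n1, r, n), taking the smallest n and then the smallest expected n under p0, gives 0/5, 0/6. This can be checked by hand.
- With n ≤ 5 the first stage has at most 4 patients. Even requiring only one response among 4 gives power of at most 1 − 0.69⁴ = 0.773, which is too low.
- With n = 6 and n1 = 5, requiring one response in the first stage gives type I error 1 − 0.99⁵ = 0.049 and power 1 − 0.69⁵ = 0.844.

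The sample size is therefore 6, not 24. With p0 = 0.01 and p1 = 0.31, varying the type I error from 0.001 to 0.20 at 80% or 90% power never gave 24 patients; the largest was 16.

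**Step 4: can the intended inputs be recovered?** Power does not depend on p0. Since power at 0.31 is 0.781, no choice of p0 makes 1/12, 5/24 an admissible design with 80% power at 0.31. Minimax designs for nearby inputs:

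| p0 | p1 | Type I error limit | Power required | Minimax design |
|---|---|---|---|---|
| 0.11 | 0.31 | 0.20 | 0.80 | 0/8, 2/13 |
| 0.11 | 0.31 | 0.05 | 0.80 | 1/16, 5/24 |
| 0.16 | 0.31 | 0.20 | 0.80 | 1/16, 5/24 |
| 0.17 | 0.31 | 0.20 | 0.80 | 1/14, 6/28 |
| 0.11 | 0.31 | 0.05 | 0.78 | 1/12, 5/24 |
| 0.11 | 0.32 | 0.05 | 0.80 | 1/12, 5/24 |
| 0.13 | 0.32 | 0.10 | 0.80 | 1/12, 5/24 |

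Each exact match changes three of the four printed inputs, and the matches disagree on the null rate and on the type I error.

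**Step 5: what the written rule does.**

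| True response rate | P(stop at 12) | P(pass) |
|---|---|---|
| 0.01 | 0.99 | 1.1e-7 |
| 0.11 | 0.61 | 0.039 |
| 0.16 | 0.41 | 0.165 |
| 0.17 | 0.37 | 0.201 |
| 0.25 | 0.16 | 0.556 |
| 0.31 | 0.07 | 0.781 |
| 0.33 | 0.06 | 0.835 |

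Solving for the null rate, the type I error equals 0.20 at p0 = 0.170, 0.10 at 0.139 and 0.05 at 0.117.

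**The case against.** The operative rule is complete and unambiguous, response rate is secondary, and safety is monitored by a separate rule, so no patient is treated differently because of the misdescription. A type I error of 1.1e-7 respects a limit of 0.20. The 0/5, 0/6 design is degenerate, since the sixth patient can never change the decision, so six against 24 is not a real choice between designs. The exact matches in Step 4 also suggest a sensible rule whose inputs were misreported, perhaps through a mistyped digit.

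Much of this stands. The damage is to interpretation rather than to conduct, the power gap is minor, and the six-patient design only shows how far the inputs are from the rule. Two things do not follow. A single wrong digit does not explain the text: reading 0.01 as 0.11 and keeping 0.20 gives 0/8, 2/13. And the existence of several matches, with nulls of 0.11 or 0.13 and errors of 0.05 or 0.10, is the reason a reader cannot settle the point. It must come from the sponsor.

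**Conclusion.** The concern holds. The printed inputs call for 6 patients, not 24, and the stated type I error of 0.20 compares with an exact 1.1e-7 at the stated null. Only p1 and power roughly fit the rule (0.781 against 0.80). These results are exact binomial calculations. They assume independent responses with a common rate, the cut-offs applied as written to 12 and then 24 patients, and the usual definition of minimax (smallest total n, then smallest expected n under the null). The documents do not show which null was intended. Because the statement is wrong as written for the only formal efficacy rule, and a reader cannot repair it, it must be corrected.

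**What to change.** Keep the rule and correct its description in Section 10.0.

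1. State and justify the intended null rate and type I error, and confirm p1 and power. The null should rest on clinical reasoning and not be picked because it fits the cut-offs.
2. Remove the claim that 1/12, 5/24 is the minimax design for the printed inputs. Use the term again only if the corrected inputs generate the rule.
3. Print the exact early-stop and pass probabilities from the table in Step 5, giving power at 0.31 as 78%.

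Optionally, add a sentence that passing does not show superiority to ibrutinib alone. The plan claims no such test. For illustration, the rule passes with probability 0.556 at the 25% response rate (20 of 80) and 0.835 at the 33% rate (5 of 15) that Section 2.2.3 reports for single-agent ibrutinib. Those rates differ by study and subtype, and the second rests on 15 patients.

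The cost is wording and numbers in one section, with no added patients and no change to the interim look or the cut-offs. If the sponsor finds the exact error at its intended null unacceptable, changing the cut-offs would be a separate decision.

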As discussed above the phase I/lb study (NCT #02006485) with ublituximab and umbralisib in rel/ref CLL and NHL continues to accrue. An amendment to this protocol allowed for the addition of ibrutinib at 560 mg daily to UTX (fixed at 900 mg) in addition to increasing doses of umbralisib. To date, safety data on umbralisib is notable for no episodes of hepatotoxicity reported with umbralisib as a single agent or in combination with ublituximab (doublet), or with ibrutinib (triplet).(10, 16, 18) In the 12 rel/ref DLBCL patients treated with umbralisib and UTX whom were eligible for response 5 patients had obtained a response and two had a PET/CT confirmed complete responses. Sixteen patients have been enrolled into the triplet regimen without a DLT in the NHL cohorts. The 800 mg dose level of umbralisib has been enrolled and completed without a DLT. Early responses have been seen in multiple NHL subtypes.

Given the safety of the umbralisib as a single agent, in the doublet and the triplet cohorts in combination with the early efficacy signal reported we propose to further explore the safety and tolerability of an all oral regimen of ibrutinib and umbralisib in patients with rel/ref DLBCL who have relapsed post-transplant or have been determined to be ineligible or unsuitable for transplant at the full doses of umbralisib (800 mg) and Ibrutinib (560 mg) in a single center open label phase IIa study.

Section 3.0 Eligibility Criteria:

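### Section 10's poor-regimen response rate of 0.01 is unsupported and conflicts with the protocol's own 25% for ibrutinib alone, so passing the efficacy rule does not show benefit over ibrutinib

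*Combined protocol and SAP*

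**What the plan says.** The efficacy rule is in Section 10.0 (Statistical Considerations). The first look reads: "After testing the combination on 12 patients, the trial will be terminated if </= 1 patients respond". The final look reads: "If the total number responding is less than or equal to five, the regimen will be rejected". The section calls this a Simon two-stage minimax design and gives as its parameters an "overall response rate for a poor regimen of 0.01, overall response rate for a good regimen of 0.31, a type I error of 0.20", with power of 80%. It gives no source for the 0.01 and does not relate the rule to the activity of either drug alone.

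The background section on the clinical activity and safety of ibrutinib (second section numbered 2.2.3) describes a phase I/II study of ibrutinib alone, started at 560 mg/day, in relapsed or refractory DLBCL: "The overall response rate (ORR) was 25% (20/80 subjects"). By subtype, the rates were 37% (14/38) in ABC and 5% (1/20) in GCB.

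Under Section 5.2 every patient in this trial takes ibrutinib 560 mg daily. Groups B and C start on Day 1. Group A adds it after Days 1 to 8 on umbralisib.

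**The concern.** The null rate of a single-arm screen should be a response rate at which the regimen would not be worth pursuing. Here the regimen contains a drug for which the protocol itself reports 25% at the same dose in the same disease. A null of 1% is far below what that component alone would be expected to give, so an error rate quoted against 1% says nothing about a doublet in which umbralisib contributes nothing.

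What is at stake is how the result may be read. The lowest count that escapes rejection is 6 of 24, which is exactly 25%. Section 10.0 wants the efficacy data as background for a powered later study. Without a stated reference rate, a pass with a quoted 20% type I error could be taken as evidence for the combination when it may reflect ibrutinib alone.

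**Working it through.** **Inputs.** From Section 10.0: 12 patients at stage 1, stop at ≤1 response; 24 in total, reject at ≤5; null 0.01, alternative 0.31, type I error 0.20, power 80%. From the ibrutinib background section: 20/80 overall, 14/38 ABC, 1/20 GCB. Responses are taken as independent binomial, all 24 patients are counted, and the separate toxicity stopping rule is ignored.

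**Formula.** With *b*(k; 12, p) the binomial probability of k responses in 12,

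P(not rejected | p) = Σ (k = 2 to 12) *b*(k; 12, p) × P(Bin(12, p) ≥ 6 − k).

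**The plan's own figures.** At p = 0.31 this gives 0.781, close to the stated 80%. At p = 0.01 it gives 1.1 × 10⁻⁷, not 0.20. A full minimax search with the stated inputs (0.01, 0.31, 0.20, 80%) returns a maximum of 6 patients, not 24. The stated null therefore did not generate these boundaries.

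**The null the boundaries support.** P(not rejected) is 0.1995 at p = 0.1695 and 0.2015 at p = 0.17, so the type I error is 0.20 at a null of about 0.17.

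**At the single-agent rate, p = 0.25.** The chance of stopping at stage 1 is 0.75¹² + 12 × 0.25 × 0.75¹¹ = 0.0317 + 0.1267 = 0.158. The chance of passing both stages is the sum of:

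- k = 2: 0.2323 × 0.3512 = 0.0816
- k = 3: 0.2581 × 0.6093 = 0.1573
- k = 4: 0.1936 × 0.8416 = 0.1629
- k = 5: 0.1032 × 0.9683 = 0.1000
- k ≥ 6: 0.0544

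The total is 0.556.

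**Dependence on the reference rate.** The exact 95% interval for 20/80 is 16.0% to 35.9%. For subtype mix, two-thirds GCB and one-third ABC (an assumption that leaves out unclassifiable cases) gives (1/3)(14/38) + (2/3)(1/20) = 0.123 + 0.033 = 0.156. An equal mix gives 0.5 × 0.368 + 0.5 × 0.05 = 0.209.

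| True response rate | P(not rejected) |
|---|---|
| 0.01 (stated null) | 1.1 × 10⁻⁷ |
| 0.156 (assumed 2/3 GCB, 1/3 ABC) | 0.15 |
| 0.160 (lower limit for 20/80) | 0.16 |
| 0.17 | 0.20 |
| 0.209 (assumed equal mix) | 0.37 |
| 0.25 (20/80) | 0.556 |
| 0.31 (stated good rate) | 0.781 |
| 0.359 (upper limit for 20/80) | 0.90 |

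**Precision of a bare pass.** An observed 6/24 has an exact 95% interval of 10% to 47%, which includes 25%.

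**The case against.** Three arguments on the other side carry weight.

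First, the 0.56 comes from the boundaries, not from the 0.01. A reader might infer that the low null causes the 56%; it does not, since the 0.01 did not produce the boundaries. The 0.01 may be a misprint: a minimax search with a null of 0.16 and the other inputs unchanged gives the same final boundary, 5 of 24, though with 16 rather than 12 patients in stage 1. The documents cannot settle this. If it is a misprint, the working gap is about 17% against 25%, much smaller than 1% against 25%. But correcting the number alone leaves the 0.56 as it is.

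Second, 25% is itself an average over subtypes. A reader might infer that, as an all-comers figure, it is free of the ABC/GCB question. It is not: the 80-patient study had 38 ABC and 20 GCB patients, while the B-cell receptor pathway section of the introduction puts GCB at nearly two-thirds of DLBCL. Eligibility does not select by subtype and the trial's mix is unknown. With two-thirds GCB the pass probability falls to about 0.15, within the stated 0.20. So a flat statement that an ineffective addition is more likely to pass than fail is not supported.

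Third, safety and tolerability are the primary objective (Section 1.0), and Section 10.0 calls the efficacy assessment preliminary. The rule stops the trial or rejects the regimen. A reader might infer that a pass is meant to show superiority to ibrutinib or to trigger a further trial; no section says so. Nor could 24 patients in one arm do it: separating 25% from 31% at the stated error rates needs about 160 patients (normal approximation 158, exact single-stage 163).

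A reader might also take the 33% (5/15) from the phase I ibrutinib study, or the 42% (5/12) for umbralisib plus ublituximab, as showing that 0.31 is too low for a good regimen. The first comes from mixed doses, the second from a different regimen, and their exact 95% intervals are 12% to 62% and 15% to 72%. Neither shows it.

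**Conclusion.** The point holds in a limited form. The null of 0.01 is unsupported, conflicts with the protocol's own single-agent figure, and does not give the stated 20% type I error with the written boundaries. That error rate holds at a null of about 0.17. If ibrutinib alone would give 25% in this trial's patients and umbralisib adds nothing, the rule fails to reject with probability 0.56; across plausible reference rates this runs from about 0.15 to 0.90. The figures rest on binomial responses, 24 counted patients, no toxicity stop, and a historical rate carried over to this population. Not being rejected is therefore no evidence that the doublet is more active than ibrutinib alone. This is a should-fix matter of stated error rates and interpretation; it does not invalidate the safety design.

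**What to change.** In Section 10.0:

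- Replace the 0.01 with the null that the boundaries support: type I error 0.20 at about 0.17, with power 0.78 at 0.31.
- Name 25% (20/80) as the single-agent reference rate, and note that it depends on subtype mix.
- Keep ≤1/12 and ≤5/24 as a futility screen only. State its probability of passing at 25% (0.56) and over the 16% to 36% range (0.16 to 0.90).
- State that passing the screen is not evidence of benefit over ibrutinib alone, and report the response rate with its exact confidence interval beside the 25%.

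I would not add a higher cut-off for claiming superiority. A bar of 9 of 24, for example, would be met only 31% of the time at the plan's own good rate of 0.31, yet 51% of the time with no added benefit if ibrutinib alone gives 35.9%.

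The cost is a few sentences, with no added patients, visits or data. The downside is that the stated error rates look less favourable and a pass supports a weaker conclusion.

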5.5 Follow-up Evaluations Course Assessment Schedule

A cycle is 28 days of treatment with any oral agent regardless of group assignment. Response assessment will be done after cycles 2, 4, 6, 9, and 12 (+/- 7 days). After Month 12, efficacy assessments should occur at the investigators discretion.

We will continue to routinely monitor safety in regards to serious adverse events as well as for toxicity trends that may be of concern.

The reason for study removal and the date the patient was removed must be documented in the Case Report Form.

Patients who discontinue therapy due to an adverse event should be followed until disease progression.

5. 6 Toxicity Assessments and Dose modifications

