5.10 Assessments

5.10.1 Disease Assessment Schedule

A dedicated PET/CT Response assessment will be done after cycles 2, 4, 6, 9, and 12 (+/- 7 days). After Month 12, efficacy assessments should occur at the investigators discretion. If a PET/CT CR (Deauville 3 or less) is seen then a CT of chest, abdomen, and pelvis with contrast can be substituted.

A restaging bone marrow biopsy may be done if a staging bone marrow biopsy was previously positive or if symptoms suggest involvement.

Patients with stable disease after 6 cycles can continue treatment if the treating investigator feels the subject is deriving benefit. Patients with progressive disease (PD) at any time are off study and will discontinue study treatment.

Patients achieving PR/CR or stable disease that are felt by the investigator to be deriving a benefit may continue until disease progression or for a maximum of 12 cycles (52 weeks of any treatment).

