5.10.2 Post Trial Assessments

Patients who go off study treatment at any time during the trial will be followed for 30 days after the last day of treatment. For all patients, drug-related SAEs and AEs will be followed until baseline or ≤ grade 1 levels. Patients who responded or maintained stable disease during the study will be followed for date of disease progression. Patients may refuse to participate in the post-trial assessments.

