5.11.5 Peripheral T-cell Characteristics

Ibrutinib and umbralisib have been described to have secondary targets of Itk and CK1ε, respectively [PMID.(22, 23) These molecules play a role in T-helper cell differentiation by promoting or inhibiting Th2 polarization, respectively. We will therefore monitor the change in T- cell characteristics using 10mL of peripheral blood in EDTA from pretreatment and day 8 and 1-month. This will include the interrogation of cytokines (IFN-y, TNF-α, IL-2, IL-4, IL-5, IL-6,

IL10, IL-13), phenotypic markers (CD3, CD4, CD25, CD45RO, CCR6, CCR7, CD27, CD127, CXCR3, HLA-DR, CD38) and intracellular transcription factors (FoxP3, T-bet, GATA3).

6.0 Measurement of Effect:

6.1 Response to therapy:

Response to therapy will be classified as complete response (CR), partial response (PR), stable disease (SD), progressive disease (PD), early death, or not evaluable. Response to therapy will be determined after cycle 2, 4, 6, 9, and 12 (+/- 7 days). After Month 12, efficacy assessments should occur at the investigators discretion.

Patients with a global deterioration of health status requiring permanent discontinuation of study treatment (taken off study) without objective evidence of disease progression will be counted as progressive disease unless a prior CR or PR has been previously documented. Every effort should be made to document the objective progression even after discontinuation of treatment. Deaths will be counted as treatment failure.

Patients will be analyzed with respect to overall survival (OS) and progression-free survival (PFS). Overall survival is defined as time from the first therapy administered on trial until death from any cause. For subjects who are still alive at the time of the study analysis or are lost to follow-up, survival will be censored at the last recorded date that the subject was known to be alive. Progression-free survival is defined as time from therapy until relapse, progression, or death from any cause. Response will be determined by the principal investigator or the co-principal investigators.

CR can be achieved at any response evaluation of umbralisib and ibrutinib.

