7.0 STUDY PARAMETERS - Test Schedule for cycle 1-12

Cycle (C) = 28 days	Screening	Cycle 1			CTE Period Cycles 2-4	Cycle 5-12	End of Treatment ⁶
Procedure \ Days (D)	21-0	Day 1 ± 3days	Day 8	Day 28	Day 1 ⁷	Day 1	
Informed consent	Χ						
Pathology confirmation of diagnosis of DLBCL or transformed DLBCL.	X						
Medical history	X						
Physical examination ¹	Χ	X	Χ		Χ	X	
Vital signs (pulse rate, BP, temperature) ¹	X	X			X	X	
ECOG performance status ¹	Χ	Χ			Χ	X	
Optional lymph node biopsy ₈		Χ	Χ				X
Mandatory Research							
peripheral blood samples 9		Χ	Χ	Χ	X9	X ⁹	X
EKG	Χ						
Serology: HCV, HBV ²	Χ						
Umbralisib	Defined by (Grouping (A,B	,C)		Daily (1-28)	Daily (1-28)	
Ibrutinib	Defined by 0	Grouping (A,B	,C)		Daily (1-28)	Daily (1-28)	
Hematology ¹	X ⁷	X	Χ		X	X	
Serum Chemistry ¹	X ⁷	Χ	Χ		Χ	Χ	
Lactate dehydrogenase (LDH)	Χ		Χ		Χ	X	
Serum Pregnancy test ³	Χ						
Radiographic Tumor Evaluation ⁴	X				X ⁵	X ⁵	

¹ Physical Exam, Vital Signs, ECOG PS, Hematology and Serum Chemistry visit days have +/- 3 day window in cycle 1 and +/- 7 day window during cycles 2-12.

²To confirm negative HBV and HCV

³ For women of child bearing potential completed within 14 days prior to Day 1 of Cycle 1

⁴Tumor evaluation must include a PET/CT; if a Deauville 3 (CR) is achieved then CT chest, abdomen and pelvis with contrast may be used. Further PET/CT scans are optional at the investigators discretion. All tumor evaluations have +/- 7 day window.

⁵ Response evaluation will occur after cycle 2, 4, 6, 9, and 12 (+/- 7 days). After Month 12, efficacy assessments should occur at the investigators discretion.

⁶ End of study will be the next visit following a cycle after study drug was administered. If a patient has completed 12 cycles of treatment without evidence of PD the patient will be monitor for relapse or progression at the discretion of the treating investigator. Follow up after 1 year of therapy will be per institutional guidelines. Patient can be taken off study to proceed to allogeneic stem cell transplant. Patients will be censored for EFS and DOR, but will be available for OS assessment.

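### Duration of response is ended at last contact rather than at the last disease assessment, so it can be overstated when contact outlasts scanning

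*Combined protocol and SAP*

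**What the plan says.** Section 10.0, in the paragraph on efficacy measures, starts DOR at documented first response and ends it at the earliest of several dates: "first response and progression, change of therapy, death, or date of last contact (if still alive without progression"). The sentence does not say which of these are events and which are censoring. The closing parenthesis makes last contact the natural censoring date. The status of change of therapy is left open.

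The other relevant text is:

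- **Overall survival (Section 6.1):** "survival will be censored at the last recorded date that the subject was known to be alive". This is the usual rule for survival.
- **PFS (Sections 6.1 and 10.0):** defined in both places, with no censoring date in either.
- **Transplant (Section 7.0, footnote 6):** for patients who leave for allogeneic transplant, "Patients will be censored for EFS and DOR, but will be available for OS assessment". No date is named.
- **Scan schedule (Section 5.5):** "Response assessment will be done after cycles 2, 4, 6, 9, and 12 (+/- 7 days"). Section 5.10.1 adds: "After Month 12, efficacy assessments should occur at the investigators discretion".
- **After treatment (Section 5.10.2):** patients are followed for 30 days, and "Patients who responded or maintained stable disease during the study will be followed for date of disease progression". No scan interval is given, and "Patients may refuse to participate in the post-trial assessments". Section 5.5 likewise has patients who stop for an adverse event followed to progression, with no interval.

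Nothing in the document ties the end of DOR to the last tumor assessment.

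**The concern.** Progression in this trial is established mainly by PET/CT or CT (Sections 6.1 to 6.5). Knowing that a responder was alive and not known to have progressed at a later visit or call does not show that the remission lasted until then. If DOR runs to that date, unassessed time counts as time in response. In a Kaplan-Meier analysis the patient stays in the risk set on dates when progression could not have been found.

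DOR is a named secondary objective, and the trial is meant to inform a later powered study. Few responders are expected: at the design's good response rate of 0.31, 24 × 0.31 is about 7. One or two patients with long unscanned contact could visibly change the curve.

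**Working it through.** The plan states no figure for DOR and names no estimator, so there is nothing to reproduce. Kaplan-Meier is an assumption here.

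**Inputs from the documents.** Cycles are 28 days, so scans fall at about weeks 8, 16, 24, 36 and 48, with gaps of 8, 8, 8, 12 and 12 weeks. Day 1 visits occur every 4 weeks. Contact after stopping treatment runs for 30 days, with longer follow-up at no set interval.

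**Inputs assumed.** First response is at week 8, so later scans fall at 8, 16, 28 and 40 weeks of DOR. True DOR is exponential with a median of 4, 6 or 10 months (1 month = 52/12 weeks). A fraction d of responders still on study leaves scanning at each scan, with d = 0.15 or 0.30. Last contact is 1 or 3 months after the last scan. Progression is dated at the scan that finds it, and nothing is found at contact.

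**Formula.** With median m weeks, the chance of progressing across a gap of g weeks is q = 1 − 0.5^(g/m).

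- Censoring at last scan: S = product of (1 − q).
- Last contact 13 weeks after the last scan: this is longer than one gap (8 or 12 weeks) and shorter than two. Those who have just left are counted at risk on the missed scan date but cannot have an event, so S = product of (1 − (1 − d)q).
- Last contact about 4.3 weeks after the last scan: they leave the risk set before the next scan date, so S = product of (1 − q), the same as for last scan.

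**Example, median 6 months (26 weeks).** For an 8-week gap q = 1 − 0.5^(8/26) = 0.192. For a 12-week gap q = 1 − 0.5^(12/26) = 0.274. By 6 months two scans have passed (DOR weeks 8 and 16):

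- last scan: (1 − 0.192)² = 0.653
- last contact, d = 0.15: (1 − 0.85 × 0.192)² = 0.700
- last contact, d = 0.30: (1 − 0.70 × 0.192)² = 0.749

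By 9 months a third scan, after a 12-week gap, is added in the same way.

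| Median | d | 6 months: last scan → last contact | 9 months: last scan → last contact |
|---|---|---|---|
| 4 months | 0.15 | 0.527 → 0.589 (+0.06) | 0.326 → 0.398 (+0.07) |
| 4 months | 0.30 | 0.527 → 0.653 (+0.13) | 0.326 → 0.479 (+0.15) |
| 6 months | 0.15 | 0.653 → 0.700 (+0.05) | 0.474 → 0.537 (+0.06) |
| 6 months | 0.30 | 0.653 → 0.749 (+0.10) | 0.474 → 0.606 (+0.13) |
| 10 months | 0.15 | 0.774 → 0.806 (+0.03) | 0.639 → 0.687 (+0.05) |
| 10 months | 0.30 | 0.774 → 0.839 (+0.06) | 0.639 → 0.736 (+0.10) |

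Simulation of the same set-up agrees. With d = 0 both rules give the same curve through the last scheduled scan.

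**A separate upward bias.** With a 6-month median the true 6-month rate is 0.50, yet the last-scan rule already gives 0.65. Progression between DOR weeks 16 and 28 is dated at week 28, so the 6-month estimate is really 0.5^(16/26) = 0.65. Only the increments in the table belong to the censoring rule.

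**Longer lags.** In a second simulation, scans stop at a hazard of 0.02 per week while contact continues to weeks 52-156 (assumed). With a 26-week median, the 40-week rate is 0.34 under last scan (truth 0.34) and 0.56 under last contact. If all scheduled scans are done and none follow Month 12, both rules give 0.34, but mean follow-up per responder is 28.0 weeks under last scan and 47.4 under last contact.

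**What the schedule allows.** On treatment with scans kept, the last visit is at most about 4 weeks after the last scan up to week 24 and about 8 weeks after it between weeks 24 and 48, plus windows. Both fall short of the next scan. After Month 12, or after stopping treatment early, the documents set no upper limit.

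**The case against.** Several points on the other side are fair.

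- **There is follow-up for progression.** Sections 5.5 and 5.10.2 and footnote 6 of Section 7.0 all provide for it, and on-treatment visits include examination and LDH. A reader might infer that the plan leaves responders unmonitored; it does not. What is missing is a scan interval.
- **The wording is conditional.** Last contact applies only to a patient without progression, which could be read as the last contact at which freedom from progression was known. The sentence does not say how that is known, so the ambiguity remains.
- **The lag and drop-out rates are assumed.** Losing 15-30% at each of four scans means 48-76% lost overall (1 − 0.85⁴ and 1 − 0.70⁴). No text supports that rate, and the 30-day contact alone adds no Kaplan-Meier bias.
- **The error need not go one way only.** A reader might infer that it must. If deaths and clinical progressions found at contact count as events, censoring everyone else back at the last scan can bias DOR downward. With a 26-week median, d = 0.15 and a 13-week lag, the true 40-week rate is 0.34. Capturing all such events gives about 0.28 under last scan and 0.33 under last contact; capturing half gives about 0.32 and 0.38.
- **Precision is poor anyway.** With 7 responders, the standard error of a rate of 0.65 is √(0.65 × 0.35/7) = 0.18, above every increment in the table.

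These points limit the size and certainty of the bias. They do not make last contact evidence of continuing remission.

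**Conclusion.** The point holds in a limited form. The stated end date for DOR can credit remission time that no disease assessment verified, and the follow-up plan lets contact outlast scanning. Under the assumed losses and a 3-month lag the added bias is about 0.03-0.13 at 6 months and 0.05-0.15 at 9 months. It is zero if scheduled scans are completed or the lag is about 1 month. It comes on top of the upward bias from dating progression at the next scan.

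A reader might also infer that PFS will be overstated in the same way. The documents do not say so: they give PFS no censoring date, and the analyst's choice is open. That is a gap to close, not a demonstrated bias.

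DOR is secondary. The response rate, the toxicity and efficacy stopping rules and N=24 do not depend on it.

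**What to change.** In Section 10.0:

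1. Censor DOR at the date of the last adequate disease assessment showing no progression, for responders alive without documented progression.
2. State whether change of therapy is an event or a censoring point, and give the censoring date for patients who leave for allogeneic transplant (Section 7.0, footnote 6).
3. Give PFS the same censoring rule.
4. Keep last-known-alive for overall survival only.
5. State that deaths and clinical progressions found after the last scan still count as events, and show a sensitivity analysis censoring at last contact, since such events can make the last-scan rule err downward.

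The cost is a few sentences. No new procedure is needed, because Section 11.1 already requires scan reports in each research chart. Reported DOR may be slightly shorter.
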